### **3.9 STUDY VARIABLES**

The main independent variable of this study is the cognitive- behavioural therapy intervention. There are other independent or predictor variables which include socio-demographic factors (age, gender, ethnicity, income, education, type of cohabitation, marital status, and distance from home to hospital), clinical characteristics (duration of symptomatic knee OA, comorbidity, treatment, and number of visits to general practitioner) and physical factor (body mass index).

Dependent or primary outcome variable of this study will be knee pain intensity, whereas functional disability and psychological outcome measures including depression, anxiety, fear- avoidance beliefs, pain catastrophising and self- efficacy in pain management level will be the secondary outcome.

### **3.10 OPERATIONAL DEFINITION OF TERMS/ VARIABLES**

Cognitive behavioral therapy refers as one of the psychological interventions that promote realistic and optimistic attitude to illness, and it encourages patients to identify advantages after development of illness or to shift from a state of compromised function to improve function. (Sharpe & Curran, 2006)

Pain refers to sensory and emotional experience of discomfort. It is usually associated with actual or threatened tissue damage and is influenced by cognitive processes as well as the social and cultural context in which it is embedded. (Sarafino, 1994)

Functional disability refers to medical condition that captures impairments, activity limitations and participation restrictions in an individual's daily life. (Katz, 1983)

Psychological refers to the important role that cognitive factors (such as beliefs about pain control and feelings of helplessness), emotional factors (such as anxiety and depression), and behavioral factors (such as pain- related social interactions and social support) (Keefe & Somers, 2010).

### 3.11 INTERVENTION PROTOCOL

Both the intervention and control group will receive standard routine care throughout the study. They have to attend clinic and physiotherapy session as usual on their fixed appointment date. However, the control group will be provided with The Knee Book (Ministry of Health, 2013) and not receive further intervention. Patients in the intervention group will be provided with The Knee Book (Ministry of Health, 2013) and to receive a three sessions of group Cognitive Behavioral Therapy (CBT) (each session will be last for two and a half hour) bi- weekly. The session will be held in a group of eight to ten patients and supervised by an experienced senior clinical psychologist ([name]) and a physiotherapist. The intervention will be delivered by physiotherapists and nurses who will receive at least one day of training specific to the trial from an experienced senior clinical psychologist with CBT experience. Each session will be audio- recorded with a written consent from the patients. Fidelity of the CBT session will be assessed for a random sample of recordings by the experienced psychologist with the Cognitive Therapy Rating Scale (Blackburn et al., 2000), which is a valid and reliable CBT rating scale. It has high internal reliability which is cronbach alpha 0.95 and good face validity. In addition, patients in the intervention group will assess the Client Satisfaction Questionnaire (CSQ-8) after the last session of group CBT received for measuring satisfaction with the therapy provided (Attkisson, 2012). It has high coefficient alpha (ranged from 0.83 to 0.93).

The outline of the Cognitive Behavioral Therapy module is prepared and modified based on Linton (2005). The CBT intervention will include an introduction, lecture (knowledge and insight), problem solving, skills training, homework assignments and a feedback of the session. An example of a knee OA patient will be applied throughout the intervention as a model for discussion and practice in problem solving, in order to enhance peer support and social bonding. Compliance with CBT is defined as attendance at the initial assessment and at least three subsequent sessions.

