groups have the advantage of participants being able to communicate or interact with each other with similar problems (Critchley, Ratcliff, Noonan, Jones & Hurley, 2007). Consequently, the group cognitive behavioral treatment in this study aims to meet the objectives of reducing pain and improving physical and psychological functioning in patients with osteoarthritis of the knee.

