### 3.5 SAMPLE SIZE ESTIMATION

The formula for calculating sample size in hypothesis testing by comparing means will be used (Lameshow et al., 1990):

$$n = \frac{2\bar{\delta}^2[Z_{1-\alpha/2} + Z_{1-\beta}]^2}{(\mu_1 - \mu_2)^2} \quad (\text{For continuous variable})$$

Where:

(a) Using an assumed expected outcome of **knee pain intensity decrease** within 6 months of therapy,

$\bar{\delta}$  = estimated standard deviation (assumed to be equal for each group) is 10.85 (Wideman et al., 2014)

$\mu_1$  = estimated mean knee pain score for at least 6 months is 16.54

$\mu_2$  = estimated mean baseline knee pain score is 20.68 (Wideman et al., 2014)

$Z_{1-\alpha/2}$  = standard error when  $\alpha = 0.05$  (95% Confidence Interval) = 1.96

$Z_{1-\beta}$  = standard error associated with power = 0.842 ( $\beta = 0.20$ )

Power ( $1-\beta$ ) = 80%

Effect size ( $ES\mu$ ) =  $\mu_1 - \mu_2 / \bar{\delta}$  where  $\bar{\delta}$  = pooled standard deviation =  $\sqrt{\delta_1 + \delta_2} / 2$

$ES\mu = 0.38$  which corresponds to  $n = 109$

Based on the above formula, the required minimum sample size for each group,  $n$  is **109**. To factor in 20% attrition, total required per group will be **131**; hence a total of **262** patients will be required for the sample in both groups.

(b) Using an assumed expected outcome of **functional disability decrease** within 6 months of therapy,

$\bar{\delta}$  = estimated standard deviation (assumed to be equal for each group) is 35.61 (Wideman et al., 2014)

$\mu_1$  = estimated mean functional disability score for at least 6 months is 59.50

$\mu_2$  = estimated mean baseline functional disability score is 74.38 (Wideman et al., 2014)

$Z_{1-\alpha/2}$  = standard error when  $\alpha = 0.05$  (95% Confidence Interval) = 1.96

$Z_{1-\beta}$  = standard error associated with power = 0.842 ( $\beta = 0.20$ )

Power ( $1-\beta$ ) = 80%

Effect size ( $ES\mu$ ) =  $\mu_1 - \mu_2 / \bar{\delta}$  where  $\bar{\delta}$  = pooled standard deviation =  $\sqrt{\delta_1 + \delta_2} / 2$

$ES\mu = 0.42$  which corresponds to  $n = 90$

Based on the above formula, the required minimum sample size for each group, n is **90**. To factor in 20% attrition, total required per group will be **108**; hence a total of **216** patients will be required for the sample in both groups.

(c) Using an assumed expected outcome of **depression level decrease** within 6 months of therapy,

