### **3.13 DATA ANALYSIS PLAN**

Data collected will be analyzed using Statistical Package for Social Sciences software (SPSS) version 21. Parametric tests (T-test, repeated measures ANOVA and correlation analysis) will be performed. P value for test of significance of results will be set at 0.05, alpha level (Type 1 error) at 0.05 (Confidence Interval of 95%). Analysis of outcomes will be by intention-to-treat where all participants who were randomized and entered the trial need to be included in the analysis in the condition to which they were assigned, regardless of whether they completed the trial, or may even have switched over to receive the incorrect treatment, per-protocol (complete case) analysis and chi square test.

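### CBT is given in groups of eight to ten, but the sample size and the named tests treat all patients as independent; any positive within-group correlation makes the standard error too small and overstates the 80% power

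*Protocol*

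**What the plan says.** **Delivery.** Section 3.11 gives the CBT arm three group sessions of two and a half hours: "The session will be held in a group of eight to ten patients and supervised by an experienced senior clinical psychologist". Physiotherapists and nurses deliver them. The same section says the shared patient example is meant to build peer support and bonding. Section 1.1 gives the reason for the format: "groups have the advantage of participants being able to communicate or interact with each other with similar problems". Controls get routine care and a booklet, with no further intervention.

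**Allocation.** Patients are randomised individually, 1:1 in blocks (3.1). Section 3.8 draws 300 names and then splits each arm into 13 subgroups of eight to ten.

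**Sample size.** Section 3.5: "The formula for calculating sample size in hypothesis testing by comparing means will be used". The primary outcome is set in 3.9: "Dependent or primary outcome variable of this study will be knee pain intensity". For that outcome the "estimated mean knee pain score for at least 6 months is 16.54" and the "estimated mean baseline knee pain score is 20.68", with a standard deviation of 10.85. The result is 109 per group, or 131 after a 20% attrition allowance. No ICC or design effect appears for this outcome or any other.

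**Analysis.** Section 3.13: "Parametric tests (T-test, repeated measures ANOVA and correlation analysis) will be performed". It adds a chi-square test and intention-to-treat and per-protocol analyses. Nothing refers to therapy group, and the limitations in 3.15 do not mention clustering.

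**The concern.** Patients who attend the same sessions and influence one another tend to have outcomes more alike than patients from different groups. In this protocol that influence is part of the treatment. Controls have no such shared exposure, so this is a partially nested design, clustered in one arm only.

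The named tests do not handle it. A t-test treats each patient as a separate unit. Repeated measures ANOVA allows for correlation within a patient over time, but not between patients in one group. If the within-group correlation is positive, the variance of the CBT-arm mean is larger than these methods estimate. Confidence intervals are then too narrow and the 5% level is exceeded. The sample size in 3.5 makes the same independence assumption, so 80% power is the best case. This applies to knee pain and to every secondary outcome compared between the arms.

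**Working it through.** **1. Reproduce the stated figure.** The difference is 20.68 − 16.54 = 4.14. The effect size is 4.14/10.85 = 0.3816, rounded to 0.38 in 3.5. With 1.96 and 0.842:

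n = 2 × (2.802/0.38)² = 108.7, so 109 per arm.

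109 × 1.2 = 130.8, so 131. The stated figures reproduce with independent patients, that is, with a design effect of 1. Power at 109 per arm is Φ(0.38 × √(109/2) − 1.96) = Φ(2.805 − 1.96) = 80.1%.

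**2. Allow for clustering in the CBT arm only.** With m patients per group and equal total variance in both arms:

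- CBT-arm design effect: DE = 1 + (m − 1) × ICC
- variance ratio of the difference, true to unadjusted: R = (DE + 1)/2
- type I error of the unadjusted test: 2 × [1 − Φ(1.96/√R)]
- power of a valid test: Φ(0.38 × √(n/2)/√R − 1.96)

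The ICC is my assumption. I take m = 9, the middle of eight to ten.

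| ICC (assumed) | DE | R | Unadjusted type I error | Power, 109 per arm | Power, 120 per arm |
|---|---|---|---|---|---|
| 0.01 | 1.08 | 1.04 | 5.5% | 78.5% | 82% |
| 0.02 | 1.16 | 1.08 | 5.9% | 77% | 81% |
| 0.05 | 1.40 | 1.20 | 7.4% | 73% | 77% |
| 0.10 | 1.80 | 1.40 | 9.8% | 66% | 70% |

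Example at ICC 0.05: √1.20 = 1.095. Type I error is 2 × [1 − Φ(1.96/1.095)] = 2 × [1 − Φ(1.789)] = 7.4%. Power is Φ(2.805/1.095 − 1.96) = Φ(0.601) = 73%. The unadjusted standard error is 1/1.095 = 0.913 of the true one, about 9% too small. Using 0.3816 in place of 0.38 raises each power by 0.3 to 0.4 points.

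The 120 column is for enrolling the 300 names in 3.8: 150 per arm × 0.8 = 120 analysed. The type I error column does not change, because more patients do not correct the standard error.

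**3. Sensitivity.**
- *Group size.* At ICC 0.05, m = 8 gives 7.1% type I error and 74% power at 109 per arm; m = 10 gives 7.7% and 72%. If a 20% loss is spread evenly so that groups shrink to 6.4 to 8, power is about 74-75%.
- *Degrees of freedom.* The table uses the normal 1.96. With 109/9, about 12 CBT groups, Satterthwaite degrees of freedom run from about 38 (ICC 0.01) to 26 (ICC 0.10). Power at 109 per arm becomes about 76%, 75%, 70% and 63%. The tabled values are therefore upper limits.

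**4. Number needed for 80% power.** With m = 9, the normal approximation and the unrounded effect size, the analysed number per arm is 113, 117, 130 and 151 at the four ICCs. After the protocol's × 1.2 this is 136, 141, 156 and 182, against the planned 131.

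**The case against.** **The size rests on an ICC that nobody has stated.** This stands. There are only three sessions and the sample size looks to six months, so a small ICC is possible. At 0.01 the effect is close to negligible. The direction holds for any positive ICC; the size is conditional.

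**Model detail belongs in the analysis plan.** This stands in part. Section 3.13 is a general list that assigns no test to the primary outcome, and an unseen plan might refine it. But the protocol names tests that do not fit the design, and the sample size is fixed in the protocol itself.

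**The 300 names in 3.8 give a margin.** They would restore 80% power at ICC 0.01 and 0.02, but not at 0.05 or 0.10. They are not described as a clustering allowance, and 13 groups of eight to ten hold only 104 to 130 patients per arm, not 150.

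**Section 3.8 also divides the controls into subgroups.** Since 3.11 gives controls no further intervention, that division appears administrative, and nesting in the CBT arm only is the better reading.

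**Stronger readings that the protocol does not support.** A reader might infer that each CBT group has its own therapists, which would be a second source of correlation. Section 3.11 does not say whether a therapist leads one group or several; the point rests on member interaction alone. A reader might also infer that the error favours a positive result for CBT. The inflation is two-sided: at ICC 0.05 the 7.4% splits into 3.7% in each direction. At the assumed effect, the unadjusted test rejects slightly less often than planned: Φ((2.805 − 1.96)/1.095) = 78.0%, against 80.1% under independence. What is overstated is precision.

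**Conclusion.** The point holds in conditional form and should be fixed. Group delivery in one arm, and a sample size and named tests that assume independence, are both plain in the protocol. If the within-group ICC is positive, which the intended peer interaction makes plausible, the unadjusted standard error is too small and the 80% power is overstated.

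Over assumed ICCs of 0.01 to 0.10, with 9 per group and 109 analysed per arm, type I error runs from about 5.5% to 9.8% and power from at most 78-79% down to 66%. With small-sample degrees of freedom power is a few points lower. If 300 patients are enrolled, power runs from about 82% to 70%, and the standard error still needs correcting.

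It would go too far to say that the 5% level will certainly be exceeded or that the trial is clearly underpowered. Both depend on a correlation the protocol does not give.

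**What to change.** 1. **Data collection (3.12).** Record the CBT group of each patient in that arm. Without it, the adjusted analysis cannot be carried out later.
2. **Analysis (3.13).** For the outcome comparisons, replace the t-test and repeated measures ANOVA with a mixed model that has a random CBT-group effect in the CBT arm only, with each control as its own unit. Keep the correlation between a patient's repeated measurements and use small-sample degrees of freedom.
3. **Sample size (3.5).** Restate power with the CBT-arm design effect 1 + (m − 1) × ICC for ICC 0.01 to 0.10, using the number to be enrolled. In doing so, reconcile the 262 patients in 3.5 with the 300 names and 13 subgroups in 3.8.

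The cost is one data field, revised wording, slightly wider confidence intervals and a lower stated power. These changes need no extra patients. Holding 80% power at a chosen ICC would be a separate decision; at ICC 0.05 it needs about 130 analysed per arm.

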### 3.12 DATA COLLECTION PLAN

A baseline measurement on patients' knee pain intensity, functional disability, psychological distress (depression, anxiety, and stress), fear- avoidance beliefs, pain catastrophising and self- efficacy in pain management will be collected on respondents in both intervention and control group prior to the introduction of CBT. The efficacy endpoint will then be measured immediately, one month and six months after intervention. A structured self- administered questionnaire which is validated and reliable would be used as the data collection tool.

The questionnaire would consist of eight sections, sections A to H (A: Patients' socio- demographic and clinical characteristics; B: knee pain intensity; C: functional disability; D: Psychological distress (depression, anxiety and stress); E: Fear-avoidance beliefs; F: Pain catastrophising; G: Self- efficacy in pain management). The measures will include:

*Knee injury and Osteoarthritis Outcome Score (KOOS)* (Roos & Lohmander, 2003) will be adapted for the measurement of knee pain intensity and functional disability. The KOOS was developed as an extension of the Western Ontario and McMaster Universities Osteoarthritis Index (WOMAC) with the purpose of evaluating short-term and long- term symptoms and function in subjects with knee injury and OA. It has 42 items in five separately scored subscales: pain, other symptoms, function in activities of daily living (ADL), function in sport and recreation and knee- related quality of life. However, only the pain, ADL and function in sport and recreation subscale will be adapted.

*Depression Anxiety and Stress Scale (DASS)* (Lovibond, 1995) will be adapted for the measurement of depression and anxiety outcomes. The DASS is a 21- item questionnaire which designed to measure symptoms of depression, anxiety and stress. Patients are required to rate the extent to which they have experienced in depression, anxiety and stress symptoms over the previous week.

*Fear- avoidance Beliefs Questionnaire (FABQ)* (Waddell, Newton, Henderson, Somerville, & Main, 1993). The FABQ is a 16- item questionnaire which had been modified to measure fear- avoidance beliefs among knee OA patients. It is designed to predict those patients that have high pain avoidance behaviour.

*Pain- related Self Statements (PRSS)* (Flor, Behle, & Birbaumer, 1993). The PRSS consists of two scales (coping strategies and catastrophising) which designed based on the concepts of the cognitive system and automatic thoughts where patients with severe pain will present these cognition symptoms. However, only pain catastrophising scale will be adapted in this study. The pain catastrophising scale consists of nine items. Higher scores indicate the presence of catastrophising thoughts.

*Pain Self Efficacy Questionnaire (PSEQ)* (Nicholas, 2007). The PSEQ is a 10 – item questionnaire which designed to assess the patients' confidence in performing activities while they were in pain.

### **3.12.1 ANTHROPOMETRIC MEASUREMENT**

A standard clinical weighing scale and height scale will be used to measure the weight and height of each patient and recorded in kilograms and centimeters respectively. Body mass index (BMI) will be calculated using the formula weight in kilograms divided by height in meter square. BMI will be categorized into normal weight (BMI of less than 24.99), overweight (BMI of between 25.00 and 29.99) and obese (BMI of more than 30.00) as according to World Health Organization BMI classification.

### **3.13 DATA ANALYSIS PLAN**

Data collected will be analyzed using Statistical Package for Social Sciences software (SPSS) version 21. Parametric tests (T-test, repeated measures ANOVA and correlation analysis) will be performed. P value for test of significance of results will be set at 0.05, alpha level (Type 1 error) at 0.05 (Confidence Interval of 95%). Analysis of outcomes will be by intention-to-treat where all participants who were randomized and entered the trial need to be included in the analysis in the condition to which they were assigned, regardless of whether they completed the trial, or may even have switched over to receive the incorrect treatment, per-protocol (complete case) analysis and chi square test.

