## 1.5 CONCEPTUAL FRAMEWORK

Covariates included age, gender and obese status (Keefe et al., 2004).

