### **3.1 STUDY DESIGN**

This study is a 2 arm randomized clinical trial involving diagnosed knee osteoarthritis patients who are eligible to the study from February 2015 to July 2015 at Hospital Putrajaya and Hospital Serdang, Selangor, Malaysia, will be conducted. The sample population will be randomly divided into experimental and control groups by applying block randomization technique in a ratio 1:1. Random allocation will consider and eliminate the possible bias based on the socio- demographic characteristics of the patients. The experimental group will receive Cognitive Behavioral Treatment (CBT) provided with The Knee Book (Ministry of Health, 2013) added to standard routine care, whereas the control group will receive standard routine care only provided with The Knee Book and follow the same schedule of assessment as the experimental group. For standard routine care, patients need to attend their clinic and physiotherapy session as usual based on their fixed appointment date. A baseline measurement on patients' knee pain intensity, functional disability, psychological distress (depression, anxiety and stress), fear- avoidance beliefs, pain catastrophising and self- efficacy in pain management will be collected on respondents in both intervention and control group prior to the introduction of CBT. The efficacy endpoint will then be measured immediately, one month and six months after intervention. Figure 3.1 shows the schematic diagram of the study design.

[figure not shown]

Figure 3 Schematic diagram of the study design

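### Section 3.13 names no baseline term, covariates, deciding test or primary visit for knee pain; one baseline-adjusted 6-month contrast would be a free improvement

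*Protocol*

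**What the plan says.** Protocol 3.13 is the only account of the outcome analysis: "Parametric tests (T-test, repeated measures ANOVA and correlation analysis) will be performed". A chi-square test is also listed, and "P value for test of significance of results will be set at 0.05". The tests are not matched to outcomes. For the ANOVA, the section does not say whether the group, time or group-by-time effect is of interest, or whether baseline is one of the repeated measures.

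Other sections bear on this:

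- **Primary outcome (3.9):** "Dependent or primary outcome variable of this study will be knee pain intensity", with no time point attached. Section 3.12 measures it with KOOS.
- **Visits (3.1, repeated in 3.12):** "The efficacy endpoint will then be measured immediately, one month and six months after intervention". None is marked as primary.
- **Baseline (3.1):** the same measures "will be collected on respondents in both intervention and control group prior to the introduction of CBT". Section 3.8 places random allocation after the baseline questionnaire, so baseline pain is a pre-randomisation variable.
- **Covariates (1.5):** "Covariates included age, gender and obese status". Section 3.9 also lists age, gender and body mass index among the predictor variables.
- **Sample size (3.5):** an unadjusted comparison of two means, with the effect framed at six months.

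**The concern.** Two things are left loose in the section that should tie them down.

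The first is precision. The baseline score is usually informative about the follow-up score on the same scale. Adjusting for it narrows the confidence interval and deals with chance imbalance between arms, without recruiting anyone. The protocol collects the score and names covariates, but neither reaches the list of tests.

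The second is the primary contrast. With three follow-up visits and at least two eligible tests, 3.13 does not say which result answers hypothesis H2 in 1.4, that the module reduces knee pain. Only the sample size points to six months, and 3.13 does not refer back to it. As written, a claim of effectiveness could be drawn from whichever visit or test turned out significant.

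**Working it through.** **Inputs from 3.5:** SD 10.85; means 16.54 and 20.68, difference 4.14; z = 1.96 (two-sided 0.05) and 0.842 (80% power). The difference is used here as a between-arm difference, as the protocol's formula uses it. The correlation r between visits is not in the document; 0.3 to 0.7 is assumed.

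**1. The plan's own figure.** n = 2 × SD² × (1.96 + 0.842)² / difference².

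- With 4.14 and 10.85: 107.9, so 108 per arm.
- With the rounded effect size d = 0.38: 2 × (2.802 / 0.38)² = 108.7, so 109 per arm.

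The stated 109 reproduces. It is an unadjusted two-sample design.

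**2. Baseline adjustment against a t-test on follow-up scores alone.** Adjustment multiplies the outcome variance by 1 − r². With 109 analysed per arm, power = Φ(0.38 × √(109/2) / √(1 − r²) − 1.96), and 0.38 × √54.5 = 2.805.

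| r | 1 − r² | 2.805 / √(1 − r²) | Power |
|---|---|---|---|
| 0 (unadjusted) | 1.00 | 2.805 | 80% |
| 0.3 | 0.91 | 2.941 | 84% |
| 0.5 | 0.75 | 3.239 | 90% |
| 0.7 | 0.51 | 3.928 | 97.5% |

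**3. The repeated measures ANOVA that 3.13 also lists.** This takes the same d and n, a constant effect over the three follow-ups, and equal correlation r between all visits. Power = Φ(effect × √54.5 / √V − 1.96), where V is the variance relative to a single visit.

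| Reading of the ANOVA | Effect | V | r = 0.3 | r = 0.5 | r = 0.7 |
|---|---|---|---|---|---|
| Group effect, mean of three follow-ups | 0.38 | (1 + 2r)/3 | 97% | 93% | 88% |
| Mean of follow-ups minus baseline | 0.38 | (1 + 2r)/3 + 1 − 2r | 83% | 93% | 99% |
| Group effect with baseline as a fourth level | 0.75 × 0.38 | (1 + 3r)/4 | 86% | 76% | 67% |

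Against 84%, 90% and 97.5% for single-visit baseline adjustment, the ANOVA may do better or worse. The protocol does not say which version is meant.

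**4. Three visits, any one counting.** If each follow-up were t-tested at 0.05 and any significant result were taken as success, the chance of at least one false positive would be 1 − 0.95³ = 14.3% with independent tests. By simulation it is 12.5%, 10.9% and 9.9% when the test statistics correlate 0.5, 0.7 and 0.8.

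**The case against.** The strongest reply is that 3.13 lists families of tests and nowhere rules covariates out. Repeated measures ANOVA can carry covariates, 3.9 lists predictors, and a separate analysis plan may supply the model terms. The covariate sentence in 1.5 is in the past tense with a citation, so it may describe the cited trial; if it does describe this one, it suggests that adjustment is intended. This stands in part: the absence of adjustment is inferred from the tests named, not stated. It does not dispose of the point, because 3.13 goes as far as choosing the tests yet does not link them to the baseline, the covariates or the visit behind the sample size.

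A reader might infer three stronger things, none of which the document supports:

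- *The plan wastes power.* This can be shown only against a t-test on follow-up scores alone. Against the listed ANOVA the answer turns on an unstated specification, and the trial meets 80% power on its own inputs.
- *None of the listed tests uses the baseline.* That is too absolute. A group-by-time ANOVA with baseline as a level would use it in part, though an omnibus test over several visits is still not one pre-stated contrast.
- *The plan carries a 10% to 12.5% type I error.* Section 3.13 permits a t-test at every visit with any one counting, but does not say this will be done. The t-test could serve baseline comparisons, with the ANOVA handling follow-up; a single omnibus test does not incur that inflation.

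**Conclusion.** The point holds as a recommended improvement, not a validity error. An unadjusted randomised comparison is sound, and 109 per arm gives 80% power under the protocol's assumptions. What 3.13 lacks is a link from its tests to the baseline score, to the covariates and to one deciding visit and test.

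Baseline adjustment would lift power to about 84%, 90% or 97.5% compared with a follow-up-only t-test. This rests on the assumed correlations, on d = 0.38 and on 109 analysed per arm. The 10% to 12.5% type I error is conditional on all three visits being tested separately with any one sufficing, and on test statistics that correlate 0.8 to 0.5. The need to name the primary contrast does not depend on the power figures.

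**What to change.** In 3.13, state the primary analysis as the between-arm difference in KOOS pain at 6 months, from a linear or mixed model adjusting for baseline KOOS pain, age, gender and obese status, tested once at two-sided 0.05. Make the immediate and 1-month differences secondary. Analyse each secondary outcome in the same form with its own baseline score. Hospital may be added as an optional covariate; the protocol does not name it as one.

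The cost is a paragraph of wording. The baseline scores, age, gender, and the height and weight behind obese status are already to be collected, so recruitment and visits do not change.
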